1. INTRODUCTION

1.1. Purpose and scope of the statistical analysis plan

The purpose of this Statistical Analysis Plan is to set out the study objectives and hypotheses, and the analytical approaches and procedures necessary to address these for the main trial paper and to provide guidance for further research reported in other papers, promoting consistent approaches and methods.

As there can typically be more than one analytical approach to address a hypothesis, there is the potential for different results to be produced from using alternative approaches, alternative methods, alternative outcome definitions and the alternative data involved in analyses. These differences can be influential, for example, when results are of borderline statistical significance or change clinical interpretation. The presence of an approved SAP enables choices to be more fully discussed and justified in advance of the data analysis.

Therefore, the approved Version 1.0 of this SAP records those decisions that can be made about study hypotheses, outcome definitions and statistical procedures, along with their basis and the appropriateness of the assumptions required for their use, in advance of the main trial analysis, while any access to follow-up data by trial arm is prevented. Changes made within any subsequent versions of the Plan prior to analysis will be listed and dated, with the basis for the changes reasoned, and recorded within the plan for re-approval (e.g. from a change to the protocol, or identification of a more appropriate analysis method).

According to the MHRA 'Grey Guide' and ICH E9, blinded reviews of trial data can be used for the development of the SAP (1, 2). These are generally between final data lock and the beginning of the final analysis. Analysis decisions can be made at an earlier point, based on viewing the observed distribution of the data. In this trial, the trial statistician will be unblinded to produce open and closed DMEC reports and the senior statistician will remain blinded to closed reports and participant arm. The analysis decisions at early review points around DMEC meetings will be made without access to the primary timepoint of analyses by arm. Other decisions may inevitably be made later, involving the blinded statistician, or potentially after unblinding. However, these will be documented by trial stage in the SAP and the final clinical report, and supported by reasoning and justification as mentioned above. It is not intended that the strategy set out in the plan should prohibit sensible practices. However, the principles established in the plan will be followed as closely as possible when analysing and reporting the trial.

1.2. Derivation of the statistical analysis plan

The present statistical analysis plan was derived from the trial protocol version no. 4.1, by the trial statistician, [name]. The trial statistician is responsible for the development of the SAP as well as for carrying out the statistical analysis for interim and final statistical reporting of the trial. The senior trial statistician will suggest revisions to the SAP and ensure an overall verification of the analysis throughout the study, in keeping with the Standardised Operating Procedures (SOPs) of the Imperial Clinical Trials Unit, including the SOP for developing the Statistical Analysis Plan.

The formation of this Plan has drawn on statistical guidance from: the ICH Harmonised Tripartite Guideline: Statistical Principles for Clinical Trial E9 and E3(2, 3), the CONSORT statement for reporting trials(4), the Committee for Medicinal Products for Human Use (formerly known as the Committee for Proprietary Medicinal Products) (5).

The first version of the plan was numbered draft version 0.1. Draft Version 0.2 incorporated comments from the Operations manager, Trial Manager, Chief Investigator and DMEC, and both statisticians having discussed points to be agreed as decisions or as queries for investigators. The plan was then sent to the TSC for comments and saved as draft version 0.3. When this was agreed and approved by sign-off it became SAP Version 1.0. Any further amendments will require a minimum of TSC approval, and involve opening up a draft version 1.1 (and if needed 1.2 and so on), and which on agreement will generate re-approved signed-off SAP Version 2.0 (and if further amended then to approved SAP Version 3.0 and so on). The signed-off SAP versions (from 1.0) will be saved in the Statistical Master File.

2. OVERVIEW OF THE CONDITION AND TREATMENT

2.1. Overview of the condition and its importance/scale

This trial aims to evaluate an intervention to prevent weight gain in adults.

Weight gain is related to many negative health outcomes. Overweight and obesity affects over 60% of the UK population and drives the prevalence of a number of common co-morbidities, including type 2 diabetes, cardiovascular disease and cancer. It is estimated that the cost of obesity to the UK economy was £27million in 2015 and this expenditure is set to rise, as 700,000 new cancer diagnoses directly caused by being overweight or obese are predicted by 2035, whilst the number of people living with diabetes in the UK has topped 4 million for the first time(6).

Weight gain occurs commonly throughout adulthood and it is adults who are at the greatest risk of substantial gains in body weight. The study intervenes in the population of adults (aged 20 to 40) who are overweight and close to obesity (having a body mass index 24-27kg/m² if South Asian, or 25-30kg/m² otherwise) who are at greatest risk of substantial increases in body weight (through recent body weight gain and/or related lifestyle behaviours that are self-reported to be low [see inclusion criteria]).

Although there has been a great focus on treatments for obesity, there has been comparatively very little on prevention. *A greater emphasis on the prevention of obesity at the population level is urgently required*, as recent findings indicate that current non-surgical obesity treatments are ineffective, as once an individual becomes obese the probability of returning to a normal body weight is extremely low (1 in 210 for men and 1 in 124 for women)(7).

A recent systematic review indicates that any treatment or strategy that can prevent the incremental upward trajectory in body weight currently observed in young adults will have significant benefits to long-term health in this population(8).

2.2. Description of the standard treatment (or placebo or current care)

The comparator intervention in this trial is a placebo supplement called inulin given to participants in 10g sachets to take one sachet per day, at any time with their normal diet for 12 months. Inulin is a naturally occurring non-digestible carbohydrate that is readily fermented by the gut microbiota in the colon. Different terms can be used interchangeably for the placebo arm, such as control, comparator, standard, inulin control, inulin placebo.

2.5. Overview of the mechanistic sub-study

A sub-sample of study participants (volunteers) will form the mechanistic sub-study. This will enable us to understand the mechanistic network behind the primary objective of the study, and the effects of inulinpropionate ester supplementation (IPE) on small changes in energy balance (colonic metabolism, appetite regulation and energy expenditure).

3. STUDY OBJECTIVES / HYPOTHESES TESTING

3.1. Principal Trial objective

The principal objective of the trial is to investigate the effect of increasing colonic propionate production through randomised supplementation of IPE on preventing weight gain, in a population of adults who are at the greatest risk of substantial increases in body weight.

3.2. Principal Research Question

The principal research question is as follows: Is weight gain after 12 months different following IPE supplementation compared to placebo inulin?

3.3. Hypotheses

The hypotheses refer to the underlying populations of relevant patients rather than the actual study subjects.

The *Working hypothesis*: The so-called "working hypothesis" is the hypothesis which motivates the trial, which the trial results may or may not support. It is that mean body weight gain is lower at 12 months followup in the IPE population compared to the inulin population.

The Statistical *Null Hypothesis*: There is no difference in mean body weight gain at 12 months in a population randomised to receive IPE compared to that randomised to receive inulin.

Statistical *Alternative hypothesis*: There is a difference in mean body weight gain at 12 months in a population randomised to receive IPE compared to that randomised to receive inulin.

3.4. Primary Objective

To measure weight gain following a 12 month intervention of IPE versus inulin control to allow between-group comparison.

3.5. Secondary Objectives

- 1. To determine the safety profile of IPE
- 2. To determine effects on glucose homeostasis as a surrogate marker of type-2 diabetes risk

- 3. To determine effects on blood lipid and cholesterol as surrogate markers of cardiovascular disease (CVD) risk
- 4. To determine effects on blood pressure as a surrogate marker of CVD and stroke risk.
- 5. To compare changes in body weight/waist/BMI/body composition during the 12 month intervention
- 6. To determine compliance (sachet count) during the 12 month intervention.

3.6. Changes in lifestyle factors

Some of the following lifestyle factors can alter weight (e.g. quitting or taking up smoking, or a marked change in physical activity), but would not be thought to have arisen from the intervention.

- 1. To compare changes in physical activity during the 12-month intervention.
- 2. To compare changes in other lifestyle factors during the 12-month intervention; smoking, drinking and recreational drugs.
- 3. To compare changes in diet during the 12-month intervention (via food diaries).

Notes:

Physical activity: Measure of level and time spent on activities by a person, according to the IPAQ Smoking: Cigarettes, cigars or vaping

Drinking: Alcoholic drinks of any type

Recreational drugs: Legal and illegal drugs taken for recreational purposes in any form

3.7. Mechanistic sub-study objectives

- 1. To explore the effects of IPE on colonic metabolism using metataxonomic analysis of the 16S ribosomal ribonucleic acid (rRNA) gene in stool samples to identify the relative abundance of the bacterial component of the microbiome.
- 2. To explore the effects of IPE on the metabolite profile using nuclear magnetic resonance spectroscopic analyses. These data will be used to determine how these specific changes in the colonic environment influence L-cell differentiation using a human organoid model.
- 3. To explore the effects of IPE on anorectic gut hormones (GLP-1, PYY, gastrin and CCK) and subjective feelings of appetite via visual analogue scales (VAS), as measures of appetite regulation.
- 4. To explore the effects of IPE on energy expenditure and hepatic lipid metabolism as potential mechanisms involved in body weight maintenance.

Notes/clarification of terms:

Insulin: Hormone produced by the pancreas and lowers blood glucose levels.

Glucagon: Hormone produced by the pancreas that raises blood glucose levels. Type 2 diabetes affects and so limits the ability of insulin to maintain the balance – when glucose goes up after food, the insulin response is not there to reduce it shortly afterwards.

Homeostasis: The state of steady internal conditions. Glucose homeostasis is a surrogate marker of Type 2 diabetes risk.

Colonic metabolism: The breakdown of products in the colon (large intestine), into metabolites.

Metabolite profile: The measurement of products of metabolism, in the gut and/or blood.

GLP-1: Glucagon-like peptide-1 is secreted by L cells in the ileum and colon, in response to a meal and enhances the secretion of insulin to maintain blood sugar levels.

PYY: Peptide tyrosine tyrosine is secreted by L cells in the ileum and colon, in response to a meal, and reduces appetite.

Gastrin: A peptide hormone which stimulates the secretion of gastric acid, from G cells in the gut.

CCK: Cholecystokinin is a peptide hormone released by the small intestine, responsible for stimulating the digestion of fat and protein. Also suppresses appetite.

Feelings of appetite: The desire to eat food.

Energy expenditure: The total number of calories (energy) that a person needs to carry out a physical function such as breathing, digesting food etc.

Hepatic lipid metabolism: Lipid metabolism by the liver - the conversion of excess carbohydrates and proteins into fatty acids and triglycerides.

3.8. Supplementary investigation

As written in the grant application, "this trial has both a pragmatic element, to answer the question of whether the policy of prescribing and uptake of inulin propionate ester as specified in the trial will reduce further weight gain compared with control, and an explanatory element to understand the mechanisms on the causal pathway of such weight change and any limitations from compliance". Therefore, we will conduct a supplementary investigation to the primary objective of the trial, where we are interested to find out whether the treatment effect may be much larger amongst a complier group of subjects. According to ICH-E9 (R1) "Supplementary analyses for an estimand can be conducted in addition to the main and sensitivity analysis to provide additional insights into the understanding of the treatment effect. They generally play a lesser role for interpretation of trial results"(10).

4. DESIGN

4.1. Study Design

This is a two-centre, double-blind parallel group randomised controlled trial with one-year follow-up that will test the superiority of inulin propionate over inulin placebo on weight gain prevention at 12-months in 270 eligible participants aged 20-40 years who are overweight but not obese and at a high risk of weight gain.

4.2. Treatment Groups

The trial is randomised with two arms and with equal allocation of participants in a 1:1 ratio to these arms. **Active Arm**: IPE for 12 months; **Placebo Arm**: Inulin for 12 months.

4.3. Eligibility Criteria

Inclusion criteria:

- 1. Males and Females aged 20-40 years
- **2.** Body Mass Index (BMI) of 24-27kg/m² if of South Asian ethnicity or 25-30kg/m² if non-South Asian, and at least one of the following:
 - A self-reported weight gain of 2kg over the last 12 months
 - Low self-reported physical activity ('low' activity as per International Physical Activity Questionnaire IPAQ)
 - Low self-reported fruit and vegetable intake (<2 servings of fruit and vegetables per day)
 - Self-reported high intake of sugar sweetened beverages (>1 serving per day)
- 3. On stable medication (if taking any) at point of screening
- 4. Written informed consent

Exclusion criteria:

- 1. Diagnosed chronic disease; Type I and II diabetes, cancer, renal failure, heart disease, organic acidaemia (propionic acidaemia, methyl malonic acidaemia)
- 2. Diagnosed gastrointestinal condition including coeliac disease, inflammatory bowel disease and irritable bowel syndrome
- 3. Previous bowel reconstruction surgery
- 4. Pregnancy or lactation
- 5. Use of antibiotics at any time in the past 3 months
- 6. Anaemic and Vitamin B12 deficient (<160 ng/L)
- 7. Taking part in a weight loss program or consuming a weight loss product
- 8. Have lost 3kg in the last 3 months
- 9. Any other gastrointestinal upset (such as diarrhoea/constipation in the last 2 weeks, abdominal cramping etc.)
- 10. Any other reason in the opinion of the investigator

4.4. Blinding

Participants will be masked to group allocation. They will receive identical-looking and identically packaged trial intervention of either active IPE or inulin control. Clinicians/outcome assessors will also be blinded to patients' treatment assignment. The trial statistician will have access to the accumulating outcome data and trial arm that is required for reporting to the DMEC. The trial statistician will attend both open and closed DMEC meetings. The senior statistician will remain blinded and attend the open meeting.

4.5. Sample Size

On the basis outlined below, a sample size of 270 randomised participants (135 per arm) was chosen to provide 90% power to detect a 2kg difference between arms in mean body weight change over 12 months using a two-sided 5% significance test, assuming a 4.35kg SD and with 25% dropout allowance.

Determination of the primary outcome effect size:

In the randomised proof of concept trial, the difference between arms in the change in body weight over 24 weeks was 1.4kg (95% CI: -0.3 to 3.1), p=0.099. Using a Bayesian method recommended for preliminary trials in which evidence in the 95% CI is translated into probabilities, there was a 95% posterior probability of an underlying positive between-arm difference favouring the intervention (11). The posterior probability of intervention-favouring differences greater than 1kg, than 1.5kg, and 2kg were respectively 69%, 47% and 25% based on 24-week intervention. The difference increased in magnitude through successive 8-week, 16-week, and 24-week timepoints. By 24 weeks there were significant reductions in the proportion of intervention participants gaining \geq 3%, and \geq 5% of body weight from a mean baseline of 90kg. We therefore chose a 2kg between-arm 12-month effect size.

Determination of the primary outcome variability:

The chosen detectable effect size of 2kg agreed with that in a weight gain prevention trial conducted over 9 months in young adults (12) by also aiming to detect a 2kg effect, and achieved 4.3kg with 81% retention. The pooled standard deviation (SD) for body weight change was 4.35kg.

Power to detect the effect:

We set a 90% power to detect the primary outcome effect size of 2kg.

Determination of the sample size based on the primary outcome:

The sample size was set to be **270 participants, 135 per arm**. This involves a 25% allowance loss of 12-month primary outcomes, and two-sided statistical testing at the 5% significance level, implying that 202 subjects are required to be followed up with a valid primary outcome. Further adjustment for baseline body weight is expected to improve the precision of the estimated treatment effect.

Power calculation for Mechanistic outcomes:

For the mechanistic studies, 34 volunteers (17 per group) would provide sufficient statistical power to detect a 15 pmol/L effect size in GLP-1 concentrations between groups, with 90% power, 5% significance value, SD 13 pmol/L. These differences are based on our previous published findings that report enhanced gut hormone release following IPE supplementation (13, 14). We therefore planned to recruit a subsample of **52 volunteers (26 per group)** to allow a 70% retention rate.

Sample size calculations were performed using nQuery Advisor 4.0 software and independently validated using Stata software.

4.6. Schedule of Time and Events

A full schedule on the timing of measures is provided in below (as in section 6.5 of protocol). The plus or minus sign are a target/guide for when the visits should happen. If any fall below/above these, the closest measurement to the visit will be used.

Assessment	Screening	Baseline/ Randomisation (1-4 weeks after screening)	2 months (+/- 2 week)	6 months (+/- 4 weeks)	12 months (+/- 4 weeks)
Consent	X				
Demographics	X				
Randomisation		Х			
Medical History	X	Х	X	Х	Х
Concomitant medications	X	Х	Х	Х	Х
Pregnancy test - females only	X	Х	X	Х	Х
Electrocardiogram (ECG)	X				
Vital signs: DBP, SBP and HR	X	X	X	Х	Х
Trial intervention		Х	X	Х	
Height, body weight, waist/hip measurements, BMI, body composition	X	Х	Х	Х	Х
Fasting blood test (glucose, insulin, lipid profile)		Х		Х	Х
Full Blood Count & Vitamin B12	X				
Food diary		Х	X	Х	Х
IPAQ	X	Х	X	X	Х
Lifestyle questions	X	X	X	X	X
Sachet count (compliance)			X	X	X
Adverse event tracking		X	X	X	X

Mechanistic evaluation

(52 ppts; Imperial site only)

(c= ppis, imperial site only)			n	•	i
Assessment	Scree ning	Baseline/Randomisation (1-4 weeks after screening)	2 months (+/- 2 week)	6 months (+/- 4 weeks)	12 months (+/- 4 weeks)
Energy expenditure (indirect calorimetry)		Х			Х
Appetite regulation (VAS, food diary, ad libitum test meal, and blood tests for anorectic gut hormones)		Х			Х
Substrate oxidation/DNL (via stable isotype tracers in water consumption) – ¹³ C breath, urine and blood samples		Х			Х
Gut microbiota (stool sample and hydrogen breath test)		Х			Х
Neuroendocrine cell number (stool sample)		X			X
Accelerometry		Х			Х

4.7. Timing of final analysis

Apart from DMEC reports, all analyses will be undertaken after the completion of the trial (last patient, last visit) (see DMP v1.0 (15)). Final analysis for the primary and secondary outcomes will be firstly reported collectively for the main report/publication of the trial. The mechanistic sub-sample study outcomes will be analyzed and reported at a later stage.

4.8. Randomisation

Participants will be randomised via a web-based randomisation system linked to the trial electronic data capture (EDC) system and database, called Sealed Envelope (https://www.sealedenvelope.com/). Randomisation will be undertaken using the method of minimisation with a random element in order to balance the arms by centre, sex, BMI within ethnicity (South Asians: 24.00-25.49 kg/m² and 25.50-27.00 kg/m² / non-South Asians: 25.00-27.49 kg/m² and 27.50 – 30.00 kg/m²) and whether they volunteer to take part in the mechanistic sub study. This will tend towards giving equal numbers assigned to both arms in each category.

5. POPULATIONS OF ANALYSIS SETS

5.1. Target Population

The *target population*, to which inferences from the end of this trial are intended to generalise, is the population of adult patients at greatest risk of substantial increase in already overweight body weight.

5.2. Trial Population

The trial population, from which the study sample is drawn, is further defined to be those adults aged 20-40 recruited from trial centres who are either South Asian with a body mass index 24-27kg/m² or non-South-Asian with a BMI of 25-30kg/m², and who had a recent body weight gain and/or related lifestyle behaviours that are self-reported to be low, and met the remaining eligibility criteria.

5.3. Trial Samples

5.3.1 Intention To Treat (ITT)

The achieved trial sample comprises those patients who consent to participate and are actually randomised into this trial. These patients are the study subjects.

This randomised trial sample is also the trial Intention To Treat (ITT) population. The intention-to-treat principle states that every subject will be analysed according to the treatment group to which they were randomised. In this trial, subjects' data will be analysed according to the *Intention to Treat Strategy* (16), under which at least one analysis of the primary outcome is recommended to be based on all individuals in the ITT population.

The trial ITT population comprises all randomised participants, regardless of eligibility (inclusion/exclusion) error, post-randomisation withdrawal, and whether the correct study treatments were received or taken, or other interventions received.

5.3.2 Mechanistic sub-sample

The mechanistic sub-sample is not a random sample of the study participants, as the eligibility is restricted to those from the Imperial study site. Those in mechanistic sub-sample will need to consent by accepting an invitation to have additional assessments at baseline and 12 months in order additionally to address the part of the research relating to mechanisms. However, inclusion in the sub-sample is determined prior to randomization, enabling randomised comparisons within the mechanistic sub-sample.

5.3.3 Compliant sample for the supplementary investigation

This refers to the supplementary investigation where we are interested to find out whether the treatment effect may be larger amongst a complier group. This sample will comprise of all subjects in the trial who were confirmed to be compliant with eligibility criteria and those in the intervention arm who were at least 50% compliant with the IPE and control subjects who were otherwise similarly compliant.

Since there are no previous studies as to what should be considered 'adherence/or compliant to the intervention', we will investigate compliance not only on those taking 50% of the sachets provided, but across a range of compliance with the trial medication from 50% to 95%, in steps of 5%.

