6.7. Compliance variables

This is of interest in itself but it is also involved in the supplementary investigation as mentioned above.

Secondary objective:	Variable	Type of variable	Timepoint(s) of evaluation of endpoint
To determine compliance during the 12-month intervention	Accountability of returned used for all subjects.	Continuous	2, 6 and 12 months

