7.7. Supplementary analysis: The effect of IPE in a more compliant population

Attributes of the supplementary and	Attributes of the supplementary analysis estimand:				
1 Population of interest: Defined by those participants eligible to be in the trial *					
2 Variable (endpoint) of interest: A	Already described in section				
3 Treatment of interest:	Already described in section 2.3				
4 Intercurrent events*:		Strategy to deal with the			
		intercurrent event:			
a) Death		Treatment policy			
b) Pregnancy/ Treatment discor	ntinuation due to pregnancy	Hypothetical strategy			
c) Concomitant 'treatment': Eg	. weight loss program /bariatric surgery/	Hypothetical strategy			
gym personal trainer					
d) AE/Development of an illnes	ss, say cancer or COVID-19 or other	Hypothetical strategy			
disease that affects participar	nts' weight				
e) Treatment discontinuation du	ue to an AE not affecting participants	Treatment policy			
weight					
f) Treatment discontinuation du	ue to lack of efficacy (increase in weight	Treatment policy			
g) Treatment discontinuation du	ue to run out of supply	Treatment policy			
h) Treatment discontinuation du	ue to being indirectly affected by	Treatment policy			
COVID-19 (preventing from	coming to clinical visits)				
5 Population-level summary for the variable: Difference in weight gain between those taking IPE and control inulin					
after 12 months					

*Just to emphasise this population is different from that addressed in section 7.2.2

In this analysis, the strategies to address the intercurrent events are the same as the ones described in section 7.2.2, except for AE or concomitant 'treatments' affecting a participant's weight, for which the hypothetical scenario is envisage. Thus, as before, measurements occurring after these events will be removed from the analysis and the LME model will be refitted.

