7.7.1 Sensitivity analysis for non-compliance

White et al. also recommend that analyses allowing for non-response and low intervention uptake (or compliance) are specified in advance in the analysis plan (24). "Incomplete uptake of trial interventions often means that randomised groups have more similar experience than the investigators had intended, which usually causes the difference in outcomes to be smaller than it would have been with better uptake." (24). This means that low compliance with the IPE may bring about two groups that have more similar intervention experience to each other than was planned (i.e. intervention more similar to control through low compliance).

Further to the previous sensitivity analysis we will conduct an analysis estimating the effect of IPE versus Inulin control on the primary outcome in a more highly compliant population, whilst respecting randomisation. This approach should provide a better estimate of the true effect without suffering from potential biases seen in a per-protocol analysis.

Therefore a complier average causal effect (CACE) analysis will be carried out as recommended and outlined by Dunn et al. (30). The Complier-Average Causal Effect (CACE) estimate is the comparison of the average outcome of the compliers in the IPE arm with the average outcome of the comparable group ("would-be compliers") in the Inulin Control arm. Since it is not well studied as to the number of sachets needed to be taken over a 12 month period for the IPE to have an effect, if there is one, alternative levels of compliance will considered, ranging from 50% to 95%, and is therefore more exploratory than the planned primary analysis. The outline of the approach to be taken is given here:

Sample sizes (N) and means (M) are deduced for the Inulin control "would-be compliers" and "would-benoncompliers" in the following table by assuming that the proportion of intervention group compliers, and control group would-be compliers, is the same under randomisation, and that would-be non-compliers in the control group would have the same mean outcome as non-compliers in the intervention group (the exclusion

restriction as	sumption). The sample sizes refer to th	ose followed-up with primary outc	ome data (bod	ly weight
at 12 months).				
Arm	Compliers	Noncompliers	All	
	(≥ chosen threshold %)	(< chosen threshold %)		

/ 1111	complicits	Noncomplicity	7.01
	(≥ chosen threshold %)	(< chosen threshold %)	
IPE	N _{I1}	N ₁₂	N
	Mil	M _{I2}	M

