Inulin Control	$= N_{c} - (N_{12}/N_{1})*N_{c}$	$= (N_{12}/N_1)^*N_C$	Nc
	$= (M_{C} - (N_{12}/N_{1})*M_{12})/(N_{11}/N_{1})$	= M ₁₂	Mc

(Statistics preceded by an "=" are unobserved, and are estimated from the observed statistics.) The method is adapted to a more plausible MAR assumption by replacing the sample sizes at follow-up by those at baseline. In the presence of missing compliance, it will be primarily assumed that the participant is a non-complier.

The CACE estimate will instead be obtained from the analysis LME model applying the strategies in table 7.7, as this adjusts for baseline and refers to the population for the supplementary investigation. The CACE estimate is the ratio of the estimated treatment effect to the proportion compliant, following the rule of thumb (31) (estimate LME/ proportion compliant).

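### Section 5.3.3 defines the supplementary sample by observed compliance in both arms, which contradicts the section 7.7 population and the CACE method in section 7.7.1

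*SAP*

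**What the plan says.** The SAP describes who is in the supplementary investigation in three places.

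- **Section 5.3.3** is the only entry under the trial samples that is defined for this investigation. It takes "all subjects in the trial who were confirmed to be compliant with eligibility criteria" and then adds a compliance condition in each arm: "those in the intervention arm who were at least 50% compliant with the IPE and control subjects who were otherwise similarly compliant". It goes on to vary the threshold from 50% to 95% in steps of 5%.
- **Section 7.7** gives the population in its estimand table as "Defined by those participants eligible to be in the trial", with no compliance condition. A footnote says that this differs from the population in 7.2.2 but does not mention 5.3.3.
- **Section 7.7.1** promises an estimate that respects randomisation, "without suffering from potential biases seen in a per-protocol analysis". It tabulates compliers, non-compliers and all participants by arm, and marks the control-arm complier and non-complier cells as unobserved. It then takes the numerator from the linear mixed effects (LME) model, applying the strategies of table 7.7, because that model "refers to the population for the supplementary investigation". Finally, "The CACE estimate is the ratio of the estimated treatment effect to the proportion compliant".

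**The concern.** A CACE and a comparison of observed compliers answer the same question by different routes. The CACE keeps everyone in the randomised arm and scales the whole-group effect by the proportion who complied. The other route selects people after randomisation by something they did, so the two groups need no longer be comparable. Section 5.3.3 describes the second route and section 7.7.1 the first.

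An analyst who builds the data set from the list of samples in section 5 and one who builds it from table 7.7 would fit the LME to different people and report different results. Only the second would meet the aim stated in 7.7.1. The investigation exists to ask whether the effect is larger among compliers (section 3.8), so an unclear choice of analysis set bears directly on its answer.

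**Working it through.** The plan states no figure for this point, so there is none to reproduce. The check is algebra on the 7.7.1 table, followed by illustrative arithmetic.

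**1. What the 7.7.1 table estimates.** Let p = N_I1/N_I be the proportion compliant in the IPE arm. The table sets the control would-be complier mean to (M_C − (1 − p)·M_I2)/p. The complier contrast is then

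M_I1 − (M_C − (1 − p)·M_I2)/p = (p·M_I1 + (1 − p)·M_I2 − M_C)/p = (M_I − M_C)/p.

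Numerical check with p = 0.7, M_I1 = 1, M_I2 = 3, M_C = 3:
- left side: 1 − (3 − 0.9)/0.7 = 1 − 3 = −2
- right side: (0.7 + 0.9 − 3)/0.7 = −1.4/0.7 = −2.

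The table and the ratio rule therefore agree. Both need M_I and M_C for whole randomised arms, and M_I2 for IPE non-compliers.

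**2. Which set supplies those quantities.**

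| Needed by 7.7.1 | 7.7 population | 5.3.3 sample |
|---|---|---|
| Mean of the whole IPE arm | yes | no, compliers only |
| Mean of IPE non-compliers | yes | no, excluded |
| Mean of the whole control arm | yes | no, compliers only |
| Proportion compliant at the threshold that defines the set | p | 1 |

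Table 7.7 also applies treatment policy to several kinds of discontinuation, while section 7.6 counts zero sachets after discontinuation. Many of the people whom 7.7 keeps would fall below the threshold and leave the 5.3.3 sample.

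**3. Size.** The SAP gives no expected p, so 0.9, 0.7 and 0.5 are assumed, with an assumed true complier effect of −2.0 kg and no effect in non-compliers. The whole-group effect is then −2.0·p.

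| p | Whole-group effect | Effect / p (7.7 set) | Compliers only, comparable controls | Compliers only, then divided by full-arm p | Factor 1/p |
|---|---|---|---|---|---|
| 0.9 | −1.8 | −2.0 | −2.0 | −2.22 | 1.11 |
| 0.7 | −1.4 | −2.0 | −2.0 | −2.86 | 1.43 |
| 0.5 | −1.0 | −2.0 | −2.0 | −4.00 | 2.00 |

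**4. Selection without any division.** Suppose the type of person who does not comply with IPE gains 1.5 kg more, and that compliance with inulin is unrelated to prognosis (both assumed). Observed control compliers then carry an excess of 1.5·(1 − p) kg, and the compliers-only contrast is −2.0 − 1.5·(1 − p):
- p = 0.9: −2.15 kg
- p = 0.7: −2.45 kg
- p = 0.5: −2.75 kg

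The true value is −2.0 kg throughout, and the whole-group effect divided by p still recovers it. A different link between compliance and prognosis could move the bias either way.

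**The case against.** The strongest reply is that the operative sections are sound and only 5.3.3 is loosely worded. The sentence in 7.7.1 that refers to the supplementary population also names table 7.7, whose first row is the all-eligible population. It says population, where the 5.3.3 heading says sample. The 7.7.1 table cannot be filled in without non-compliers, and missing compliance is classed there as non-compliance, not as a reason for exclusion. Most of this stands: 7.7 was probably the intended set.

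A reader might infer that the SAP instructs a double correction, with a compliers-only effect divided again by the proportion compliant. The documents do not support that. Applied consistently, the 5.3.3 sample has a proportion compliant of 1 at its own threshold, so the division changes nothing. The factor 1/p needs a compliers-only numerator combined with a full-arm denominator, and no section asks for that.

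Two softer readings of 5.3.3 are less convincing. The similarly compliant controls could be meant as latent would-be compliers. But 5.3.3 defines a sample of actual subjects, sachet compliance is recorded in both arms (section 6.7: "Accountability of returned used for all subjects"), and 7.7.1 itself treats control compliers as unobserved, so they could not be picked out. Reading the conjunction in 5.3.3 as a union with all eligible subjects would make the compliance condition largely redundant.

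The analysis is also supplementary and described as exploratory. That limits the weight of the point but does not remove the contradiction.

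**Conclusion.** The point holds as a contradiction between sections. Section 5.3.3 names a per-protocol set for an analysis that 7.7 and 7.7.1 define on all eligible participants and that is valid only there. The reference in 7.7.1 favours table 7.7 without excluding the 5.3.3 set.

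Using the 5.3.3 set would give a contrast between groups selected after randomisation. Its bias cannot be sized from the documents; under the assumptions shown it is 0.15 to 0.75 kg on a true −2.0 kg. Correcting twice is a further possibility that arises only from mixing the two sets. The factor would be about 1/p, or 1.11 to 2.0 for p from 0.9 to 0.5, and it is that simple only if control compliers are comparable. The 1/p factor and the selection figures therefore rest on different assumptions and should not be presented as one combined size.

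The primary estimand, the primary analysis and the sample size are not touched. The text should be corrected because the named set conflicts with the SAP's own stated aim.

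**What to change.** - In 5.3.3, replace the compliance-based sample with the set implied by 7.7: all randomised participants confirmed eligible at baseline, analysed in their randomised arm, regardless of compliance. Change the heading to match, and keep the list of thresholds as levels at which compliance is assessed, not as conditions for entry.
- In 7.7, refer to 5.3.3 for the population, so that there is a single definition.
- In 7.7.1, state that the LME numerator is fitted to this set with the table 7.7 strategies, and that compliance at each threshold from 50% to 95% enters only through the IPE-arm proportion in the denominator.

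The cost is about one paragraph in a SAP amendment. No extra data are needed, and the primary analysis does not change.
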